5.1.2 Duration of exposure

Duration of exposure (days) = (last date of exposure to investigational drug) – (date of first administration of investigational drug) + 1

Table 5-1 Imputation of Last dates date of exposure

Scenario	Rule
Investigational drug with a period administration	The planned end date of the last period in which the last non-zero dose of the investigational drug was last administered. Note: If the subject died or was lost to follow-up before the derived last date, the last date of exposure to investigational drug is the date of death or the date of last contact, respectively. If the derived last date of exposure goes beyond the data cutoff date, it should be truncated to the date of data cutoff.
Daily administration of the investigational drug	Date of last administration of a non -zero dose of the investigational drug

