## **10.3 Treatments (everolimus treatment, concomitant therapies, exposure)**

For patients in Study CRAD001M2305, the duration of everolimus exposure and cumulative everolimus dose will be described using descriptive statistics on the Safety Set.

The total duration of everolimus exposure will be calculated as the total duration of everolimus exposure received while on Study CRAD001M2301 plus the total duration of (commercially supplied) everolimus exposure reported in Study CRAD001M2305.

Similarly the cumulative dose of everolimus will be calculated as the cumulative everolimus dose received while on CRAD001M2301 plus the cumulative everolimus (commercially supplied) dose reported in CRAD001M2305.

In the CRAD001M2305 study:

- the duration of (commercially supplied) everolimus exposure will be estimated based on the dates of the first and last everolimus doses and the investigator summary of treatment interruptions (estimation of number of missed doses) between each visit.
- the cumulative dose will be estimated through the prescribed doses recorded at each visit. Between two consecutive visits, the prescribed dose will be assumed constant taking into account the investigator summary of treatment interruptions between each visit.

All exposure data will be listed.

Concomitant medications and significant non-drug therapies taken concurrently with everolimus will be listed and summarized by ATC class, preferred term by means of frequency counts and percentages.

The Safety Set will be used for all above-mentioned tables and listings.

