2.1 Definitions

2.1.1 Date of first administration of everolimus

For CRAD001M2305 patients, the date of first administration of everolimus is defined as the first date when a non-zero dose was administered in the parent study CRAD001M2301. This date was recorded on Study History (HIS) Case Report Form (CRF) of the CRAD001M2305 study.

For the sake of simplicity, the date of first administration of everolimus will also be referred to as the *start of everolimus*.

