2.1.2 Date of last administration of everolimus

For CRAD001M2305 patients, the date of last administration of everolimus is defined as the last date when a non-zero dose was administered and was recorded on the Everolimus prescription record CRF of the CRAD001M2305 study.

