3.6 Study treatment

For CRAD001M2305 patients, all data described below will be pooled with the corresponding data from Study CRAD001M2301 and will be summarized using the safety set.

The participation in this study does not require the administration of everolimus. In such cases in which the patient was taking everolimus, data collection (such as therapeutic drug trough level, duration of everolimus interruptions and everolimus prescribed dose) will only be recorded, when available.

For patients in Study CRAD001M2305, the duration of everolimus exposure and cumulative everolimus dose will be described using descriptive statistics on the Safety Set.

The total duration of everolimus exposure will be calculated as the total duration of everolimus exposure received while on Study CRAD001M2301 plus the total duration of (commercially supplied) everolimus exposure reported in Study CRAD001M2305.

Similarly, the cumulative dose of everolimus will be calculated as the cumulative everolimus dose received while on Study CRAD001M2301 plus the cumulative everolimus (commercially supplied) dose reported in Study CRAD001M2305.

All exposure data will be listed.

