3.12 Subgroup analysis

For the CRAD001M2305 patients, if the number of patients is sufficient, the following subgroups by duration of everolimus exposure will be used for some analyses:

- Less than 5 years of everolimus exposure (< 5 years)
- Between 5 years and 10 years of everolimus exposure (≥ 5 years - < 10 years)
- Ten years or more of everolimus exposure (≥ 10 years)

Note: if there are insufficient numbers of patients in one of the groups the categories may be collapsed or redefined.

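### SAP 5.1.2 measures everolimus exposure as a first-to-last span with no deduction for interruptions, contrary to protocol 10.3; read with SAP 2.1.1 and 2.1.2 it also counts the off-drug gap between studies

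*SAP*

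**What the plan says.** SAP 5.1.2 gives a single formula: "Duration of exposure (days) = (last date of exposure to investigational drug") minus the date of first administration, plus 1. For a drug taken daily, Table 5-1 defines the last date as "Date of last administration of a non -zero dose of the investigational drug". Neither has a term for interruptions or mentions that treatment runs across two studies.

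The two dates are defined earlier in the SAP. Section 2.1.1 takes the first administration as "the first date when a non-zero dose was administered in the parent study CRAD001M2301". Section 2.1.2 takes the last administration as a non-zero dose that "was recorded on the Everolimus prescription record CRF of the CRAD001M2305 study".

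Two other sections build the total differently:

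- SAP 3.6 takes the duration in M2301 "plus the total duration of (commercially supplied) everolimus exposure reported in Study CRAD001M2305". It notes that interruptions are recorded when available but gives no rule for using them.
- Protocol 10.3 has the same sum. It estimates the M2305 part from the first and last dose dates together with "the investigator summary of treatment interruptions (estimation of number of missed doses) between each visit".

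SAP Section 4, which lists changes from the protocol analyses, covers only pharmacokinetics and the indirect comparison.

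**The concern.** The SAP contains two definitions of total exposure that generally give different answers, and the one written as a formula is the one a programmer is likely to code. That formula leaves out information the protocol collects for this purpose: protocol 4.1, 6.3.2 and Table 7-1 all ask for a summary of interruptions at each visit while the patient is on drug.

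Total duration is summarised unconditionally on the Safety Set (SAP 3.6). It also defines the subgroups in SAP 3.12 (<5, 5 to <10, and 10 years or more). It is a covariate in the exploratory regressions for height or BMI abnormality (3.8.1), Tanner Stage V (3.8.2) and potential delayed puberty (3.9.2). An inflated duration can put a patient in a higher exposure group. A missing one would drop a patient whose M2301 exposure is known.

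**Working it through.** The documents state no exposure figure, so there is none to reproduce. The check compares the rules algebraically and then on assumed patients.

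**Inputs from the documents**

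- First dose in M2301 (SAP 2.1.1); last dose from the M2305 prescription record (SAP 2.1.2).
- M2301 treatment may end up to 6 months, about 183 days, before M2305 enrollment (protocol 5.1). I found no limit on the time from enrollment to the first commercial dose.
- Some patients are expected to stop everolimus at the end of M2301 and remain eligible (protocol 2.1).
- Subgroup cuts at 5 and 10 years (SAP 3.12); 15 patients (SAP 4.2).

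**Notation**

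- T1 = first-to-last duration in M2301
- T2 = first-to-last duration on commercial drug
- G = off-drug days between the two
- I = interrupted days reported in M2305

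**Rules**

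- (a) SAP 5.1.2 with the 2.1.1 and 2.1.2 dates: T1 + G + T2
- (b) SAP 3.6 sum by study: T1 + T2
- (c) Protocol 10.3, reading use of the interruption summary as a deduction: T1 + T2 − I

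Hence (a) − (b) = G and (a) − (c) = G + I. If 5.1.2 is applied within each study and the results are added, it gives (b). The gap drops out, but (b) − (c) = I remains.

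**Assumed patients** (only the 183-day limit comes from the documents; 1 year = 365.25 days; 4 years = 1461 days)

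| T1 + T2 (years) | G | I | (a) days | (b) days | (c) days | (a) − (c) |
|---|---|---|---|---|---|---|
| 4 + 4 | 0 | 0 | 2922 | 2922 | 2922 | 0 |
| 4 + 4 | 183 | 0 | 3105 | 2922 | 2922 | 183 (6.3% of (c)) |
| 4 + 4 | 183 | 90 | 3105 | 2922 | 2832 | 273 (9.6%) |
| 4 + 4 | 365 | 180 | 3287 | 2922 | 2742 | 545 (19.9%) |
| 4 + 0.8 | 183 | 60 | 1936 (5.30 y) | 1753 (4.80 y) | 1693 (4.64 y) | 243 (14.4%) |
| 4.5 + 5.2 | 183 | 60 | 3726 (10.20 y) | 3543 (9.70 y) | 3483 (9.54 y) | 243 (7.0%) |
| 4.5 + none | – | – | no last date | 1644 (4.50 y) | 1644 (4.50 y) | not defined |

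The 365-day gap assumes a delay between enrollment and the first commercial dose on top of the 6 months.

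**Reading the table**

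- The rules agree only when there is no gap and no interruption.
- Rows 5 and 6 cross the 5-year and 10-year cuts under (a) but not under (b), so the gap moves these patients. Under the within-study reading, a patient with 60 interrupted days crosses a cut only if net exposure lies within 60 days (60/365.25 = 0.16 year) below it.
- Under the within-study reading, the excess from interruptions alone is 90/2832 = 3.2% in row 3 and 180/2742 = 6.6% in row 4.
- The last row has no value because 2.1.2 needs a record on the M2305 prescription form. The cut-off-date imputation in SAP 2.2 does not help, since it applies to an existing prescription record with a missing or late end date.
- One patient in the wrong subgroup is 1/15 = 6.7% of those enrolled.

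**The case against.** The best defence is that SAP 3.6 already states the right total and that 5.1.2 is generic text. Section 5.1.2 sits under a heading on imputation, covers period dosing, and refers to an investigational drug that this study does not supply. Applied within each study and added as 3.6 directs, it would count no gap. A patient never on commercial drug would have the M2301 duration plus nothing. Table 5-1 taken alone could also accept the last M2301 dose.

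This stands as a possible reading, so the gap and the missing last date follow from the SAP's definitions rather than being unavoidable. But the SAP never says to apply the formula by study, and it defines neither a last M2301 dose date nor a first commercial dose date. The defence also does nothing for interruptions, which 5.1.2 ignores on either reading.

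Several stronger inferences are tempting, and the documents do not support them:

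- **That cumulative dose has the same fault.** SAP 5.1.3 sums dated dose records and uses non-zero doses. The gap does not enter, and interruptions held as zero-dose records add nothing. Only interruptions held solely in the investigator summary could be missed.
- **That every exposure-response analysis is affected.** The Cmin splits in SAP 3.10 do not use duration. The duration subgroups and regressions depend on sufficient numbers, and most also on a high abnormality rate. With 15 patients many may never be run.
- **That the error flattens any relationship.** This is not shown. A uniform proportional inflation only rescales a continuous covariate and leaves the strength of association unchanged.
- **That M2301 interruptions must also be deducted.** Protocol 10.3 applies the interruption summary to the M2305 part only.

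**Conclusion.** The point holds and should be corrected. What is certain is that SAP 5.1.2 omits the interruption rule in protocol 10.3 and that Section 4 does not declare the change. The overstatement of M2305 exposure equals the interrupted days.

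On the dates in SAP 2.1.1 and 2.1.2, the formula further adds the off-drug gap and leaves never-commercial patients without a value, against SAP 3.6. That part rests on reading the sections together as written.

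The 183 to 545 days (6% to 20%) rest on assumed gaps and interruptions. Six months is an eligibility limit, not an observed gap, and protocol 2.1 expects most patients to continue treatment. The 6.7% per patient assumes all 15 are in the Safety Set; a larger share of a subgroup cannot be given, because subgroup sizes are unknown.

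The consequence is confined to the descriptive exposure table and to conditional, exploratory analyses by duration. The primary height and BMI SDS, Tanner Stage V and endocrine summaries do not use this quantity.

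**What to change.** 1. In SAP 5.1.2, state that total duration is the M2301 exposure duration plus the M2305 commercial exposure duration, with the formula applied within each study. The M2305 part is net of interruptions reported in the investigator summary, as in protocol 10.3.
2. Set the M2305 part to 0 for patients with no commercial dose.
3. Amend SAP 2.1.2 so that for those patients the last administration is the last M2301 dose.
4. In SAP 5.1.3, deduct M2305 interruptions that are held only in the investigator summary and not as zero-dose records.
5. If the span is what is intended, declare it in SAP Section 4 as a departure from protocol 10.3 and say that it includes time off drug.

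The cost is SAP wording and the matching derivation code. The M2305 interruption summaries are already requested at each visit, although they are estimates recorded when available, so some days will remain approximate.

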5.1.3 Cumulative dose

Defined as the sum over the daily doses of all days between first and last dose.

Cumulative dose = sum of (daily dose at a visit * (end date of dose – start date of dose +1)).

- The planned cumulative dose total planned dose as per the protocol up to the last administration of study treatment.
- The actual cumulative dose refers to the total actual dose administered, over the duration for which the subject is on the as documented in the Dose Administration eCRF.

For subjects who did not take any drug the cumulative dose is by definition equal to zero.

The actual cumulative dose is the sum of the non-zero doses recorded over the dosing period and the planned cumulative dose is the planned starting dose summed over the same dosing period.

5.1.4 AE, concomitant medication and other safety assessment date imputation

Every effort will be made to get the missing information on partial dates. However, despite best efforts, some partial dates might still exist in the database. They will be listed as is. If needed in a calculation (e.g. duration), the standard Novartis Oncology imputation rules will be used.

Table 5-2 Imputation of start dates (Adverse events, Concomitant Medications)

Missing Element	Rule
day, month, and year	No imputation will be done for completely missing dates
day, month	If available year = year of study treatment start date then If stop date contains a full date and stop date is earlier than study treatment start date then set start date = 01JanYYYY Else set start date = study treatment start date. If available year > year of study treatment start date then 01JanYYYY If available year < year of study treatment start date then 01JulYYYY
Day	If available month and year = month and year of study treatment start date then If stop date contains a full date and stop date is earlier than study treatment start date then set start date= 01MONYYYY. Else set start date = study treatment start date. If available month and year > month and year of study treatment start date then 01MONYYYY If available month and year < month year of study treatment start date then 15MONYYYY

Table 5-3 Imputation of end dates (Adverse events, Concomitant Medications)

Missing Element	Rule For patients who discontinued study: *=last treatment date plus 30 days not > (death date, cut-off date) For patients still on study: *= last contact date on study
day, month, and year	No imputation will be done for completely missing dates
day, month	If partial end date contains year only, set end date = earliest of 31DecYYYY or end date of the on-treatment period*
day	If partial end date contains month and year, set end date = earliest of last day of the month or end date of the on-treatment period*

Any AEs and ConMeds with partial/missing dates will be displayed as such in the data listings.

Any AEs and ConMeds which are continuing as per data cut-off will be shown as ‘continuing’ rather than the end date provided.

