### **7.1.3 Study completion**

Patients will meet the criteria for study completion upon demonstrating Tanner Stage V, or reaching age 16 (females) or age 17 (males), whichever comes first. Upon meeting the criteria for study completion, the patient should schedule an End of Study visit at the site. The End of Study visit cannot be completed via telephone contact.

Patients who discontinue commercial everolimus should continue study participation until meeting any of the aforementioned criteria for study completion. The discontinuation of everolimus will be recorded on the End of Treatment CRF page. Safety monitoring should be continued for at least 30 days following the last dose of everolimus.

Patients who complete the study, or discontinue the study early, should have the reason for exiting the study recorded on the Study Phase Completion Disposition CRF (SEC) page.

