2.2 Data included in the analysis

This Study CRAD001M2305 is a long-term safety follow-up study and statistical analyses will be primarily descriptive for all endpoints. The planned statistical analysis is described in Section 10 of the protocol.

Data collected for the patients enrolled in this CRAD001M2305 study will be pooled with the corresponding data previously collected in the parent CRAD001M2301 study for the same patients, in particular, background information on the disease history, demographics and baseline characteristics, everolimus exposure, sexual and growth development data. This pooling will allow for the following:

- Obtaining baseline values collected in CRAD001M2301 before start of everolimus
- Calculating the whole exposure to everolimus for patients enrolled in the CRAD001M2305 study
- Considering the whole growth/development course over time from the start of everolimus.

The descriptive analyses of data from the CRAD001M2305 study and TOSCA registry will be presented, side by side, whenever similar data are collected in both studies. This is intended to facilitate the interpretation of the CRAD001M2305 results and help describe any potential impact of everolimus on growth and sexual development, in the TSC population, whose growth and sexual development independent of exposure to systemic mTOR inhibitors is not well characterized.

Table 2-2 summarizes the data which will be included in all the analyses described in the SAP.

Table 2-2 Data included in each analysis

Endpoints	Studies			Analysis Set
	CRAD001M2305	CRAD001M2301	TOSCA	
Baseline characteristics	X	X	X	FAS and FAS Puberty
Patient disposition	X			FAS
Protocol deviations	X			FAS
Concomitant therapy	X	X		Safety Set
Height and BMI	X	X	X	FAS
Tanner stage	X	X	X	FAS puberty
Endocrines	X	X	X	FAS
Adverse events	X	X		Safety Set
Age at menarche	X	X		Safety Set
Age at thelarche	X	X		Safety Set
Age at adrenarche	X	X		Safety Set
Potential delayed puberty	X	X		Safety Set
TAND checklist	X		X	FAS
Indirect comparison	X	X	X	FAS and FAS puberty

Endpoints	Studies			Analysis Set
	CRAD001M2305	CRAD001M2301	TOSCA	
Treatment exposure	X	X		Safety Set
Pharmacokinetics	X	X		Safety Set

In order to ensure all data in the trial is captured, the cut-off date for final analysis will be fixed to the date of the last patient last visit. For the purpose of the final analysis, all tables, figures and listings (TFLs) described in this SAP as well as in TFL shells will be produced.

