3.7 Concomitant therapy

For CRAD001M2305 patients, all data described below will be pooled with the corresponding data from Study CRAD001M2301. Concomitant medication ongoing at the time of enrollment in CRAD001M2305 and during the study will be summarized. Medications used at time of CRAD001M2301 will be listed.

Concomitant therapy will be described using the safety set.

Concomitant therapy is defined as all interventions (therapeutic treatments and procedures) besides everolimus that were administered to a patient preceding or coinciding with everolimus intake.

Concomitant medications entered into the database will be coded using the WHO Drug Reference List to allow for categorization by preferred term (PT). In addition to categorizing medication data by PT, drugs are classified according to their Anatomical Therapeutic Chemical (ATC) classification in order to present and compare how they are being utilized. The ATC classification allows for a summary of medications by a high-level common drug class.

Concomitant medications and significant non-drug therapies taken concurrently with everolimus will be listed and summarized by ATC class and PT by means of frequency counts and percentages. These summaries and listings will include medications starting on or after the start date of everolimus, or medications starting prior to the start date of everolimus and continuing after the start date of everolimus. Medications starting more than 30 days after the last day of everolimus will be only listed.

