3.9.1 Adverse events

AEs which will be counted for a specific period are those which are **treatment-emergent**. These events are those with an onset on or after the start of the treatment period, or which were present prior to the start of the treatment period but increased in severity or developed into SAEs after the start of the treatment period.

AEs collected during the CRAD001M2305 study will be described. All listings and tables will be presented for all CRAD001M2305 patients using the Safety Set.

For CRAD001M2305 patients, using the Safety Set, the overall observation period will be divided into two mutually exclusive segments:

1. everolimus exposure period: from day of first commercial dose received in the CRAD001M2305 study to 30 days after the last commercial dose received in the CRAD001M2305 study.
2. post-everolimus exposure period:
 - starting at day 30+1 after the last commercial dose received in the CRAD001M2305 study
 - or
 - starting at the enrollment date for patients who will stop everolimus in CRAD001M2301 and who will not start commercial everolimus.

The safety summary tables will include only assessments collected during the everolimus exposure period. The safety listings will include all assessments, with those collected during the post-everolimus exposure period being flagged.

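### SAP Table 5-3 caps partial AE and medication end dates at last treatment plus 30 days, so records starting later than that in off-drug follow-up can be ended before they begin (minor)

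*SAP*

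**What the plan says.** SAP 5.1.4, Table 5-3, covers adverse events and concomitant medications. When only the year is known: "If partial end date contains year only, set end date = earliest of 31DecYYYY or end date of the on-treatment period". When month and year are known: "set end date = earliest of last day of the month or end date of the on-treatment period". Completely missing dates are not imputed.

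The table header defines the end of the on-treatment period in two branches. For patients who discontinued the study it is "last treatment date plus 30 days not > (death date, cut-off date"). The other branch reads "For patients still on study: *= last contact date on study".

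Four other provisions bear on the rule:

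- Protocol 7.1.3: "Patients who discontinue commercial everolimus should continue study participation until meeting any of the aforementioned criteria for study completion". Those criteria are Tanner Stage V, or age 16 for girls and 17 for boys.
- Protocol 4.1 records concomitant medication at every 3-monthly and annual visit until the study ends, not until 30 days after the last dose.
- SAP 3.9.1 foresees patients with no M2305 dosing at all. Their post-everolimus period is the one "starting at the enrollment date for patients who will stop everolimus in CRAD001M2301 and who will not start commercial everolimus".
- SAP 2.2: "the cut-off date for final analysis will be fixed to the date of the last patient last visit".

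SAP 5.1.4 says partial dates are listed as they stand and imputed only when a calculation needs them. It gives duration as its example.

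**The concern.** A limit of last dose plus 30 days suits a trial in which follow-up stops about a month after dosing. In such a trial a record rarely starts after the limit. M2305 is built differently: off-drug follow-up can last years, and some patients may take no everolimus in it.

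Taking the earlier of the two limits then replaces a recorded year or month with an earlier date that contradicts it. Table 5-3 does not compare the imputed end with the record's start. SAP 5.1.1 does make that comparison for dose end dates, resetting an imputed end that precedes treatment start.

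Three things are exposed:

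- any AE or medication duration that is calculated;
- the prevalence over time of treatment-emergent AEs in Protocol 10.5.1.2, if it is produced;
- under further conditions, whether a medication counts as ongoing at enrolment (SAP 3.7).

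**Working it through.** The plan states no figure to reproduce, so the check applies the rule literally. The documents give no patient dates; all dates below are illustrative assumptions.

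**1. Which branch applies.** The cut-off is the date of the last patient's last visit, so no patient is still on study and the last-contact branch is empty. Protocol 7.1.3 distinguishes patients who complete from those who leave early. Table 5-3 mentions only those who discontinued and those still on study. Completers therefore fall under the 30-day cap or under no rule.

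**2. Formula under the cap.** Let L be the last treatment date. Then

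imputed end = min(31 December or month end, L + 30 days, death, cut-off).

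If a record starts s days after L and the L + 30 limit is the earliest, then

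duration = (L + 30) - (L + s) + 1 = 31 - s days.

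For s of 31 or more, the end precedes the start.

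**3. Year-only end dates.** L = 15-Mar-2017, so L + 30 = 14-Apr-2017. Each record's recorded end year is the year in which it starts.

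| Record start | s | Imputed end | Duration (days) |
|---|---|---|---|
| 5-Dec-2016 | -100 | 31-Dec-2016 | 27 |
| 15-Mar-2017 | 0 | 14-Apr-2017 | 31 |
| 14-Apr-2017 | 30 | 14-Apr-2017 | 1 |
| 15-Apr-2017 | 31 | 14-Apr-2017 | 0 |
| 15-Mar-2018 | 365 | 14-Apr-2017 | -334 |
| 10-May-2019 | 786 | 14-Apr-2017 | -755 |
| 15-Mar-2020 | 1096 | 14-Apr-2017 | -1065 |

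Check of the 10-May-2019 row: 14-Apr-2017 to 10-May-2019 is 730 + 26 = 756 days, so end - start + 1 = -755. The last three rows also end outside their recorded year. Knowing the month does not help: a record ending in April 2020 also gets 14-Apr-2017.

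The first row is unaffected because the calendar limit comes first. The second and third rows do not invert but are shortened: 31 days against 292 to 31 December, and 1 against 262.

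**4. Patients with no M2305 prescription record.** SAP 2.1.2 takes the date of last administration from the M2305 prescription form. For these patients no such date exists and the cap is undefined.

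If a programmer used the last M2301 dose instead, with enrolment g days later, then cap minus enrolment = 30 - g days. Protocol 5.2 allows treatment within the past 6 months, about 183 days. So g = 31 gives -1, g = 91 gives -61, g = 150 gives -120 and g = 183 gives -153. Only under that substitution does an imputed end fall before enrolment.

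**5. Which outputs use the imputed end.** SAP 3.9.1.4 plans patient counts by class, term and grade. SAP 3.7 plans medication counts and percentages. Neither tabulates durations.

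The consecutive-event count in SAP 3.9.1.6 does use end dates, but only for treatment-emergent events. If a later event with the same term also starts by L + 30, an earlier event ended at L + 30 still reaches it, so the two still form one block.

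The protocol's prevalence analysis depends on end dates. Events still running after the drug was stopped would leave it at L + 30. The SAP's list omits that analysis, and SAP Section 4 does not record dropping it.

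**The case against.** The strongest reply is that the impossible dates reach no planned table. Inversion needs a start 31 or more days after the last dose. SAP 3.9.1 and 3.9.1.3 keep such AEs out of the summaries, and SAP 3.7 only lists medications that start that late. The listings show the partial date as recorded. This stands, and it is why the point is minor.

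Other parts of the reply also stand, and rule out readings a reader might be tempted by:

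- **AEs of patients never on commercial everolimus drop out of the summaries because of the rule.** They have no exposure period in M2305, so their AEs are outside those tables by design.
- **Imputed ends fall before enrolment.** SAP 2.1.2 supplies no last treatment date for those patients; the result needs the last M2301 dose in its place.
- **Medications vanish from the SAP 3.7 table.** The plan says "Concomitant medication ongoing at the time of enrollment in CRAD001M2305 and during the study will be summarized" but not that this status is derived from an imputed end. Another criterion in the same section, continuing after the start of everolimus (the first M2301 dose), would still be met.
- **On-drug and off-drug patients are made to differ.** No such comparison of AEs or medications is planned.
- **The cap governs every patient at the final analysis.** Completers are not clearly assigned to it.

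SAP 2.2 also refers partial-date details to programming specifications, which are not among the documents and may contain a start-date check. That does not cure the rule as written, which returns an impossible value in the calculation SAP 5.1.4 names.

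**Conclusion.** Table 5-3 is wrong as written for a study with off-drug follow-up, and the consequence is minor. Under the cap, every record that starts 31 or more days after the last dose and has a partial end date is given an end before its start. Records that start earlier are cut short whenever their calendar limit lies beyond last dose plus 30 days. Completers have no clear branch, and patients without an M2305 prescription record have no defined cap.

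The affected results are any calculated durations and the protocol's prevalence over time if it is produced. The ongoing-at-enrolment status in SAP 3.7 is affected only if the last M2301 dose is used as the last treatment date and the imputed end decides the status. Planned AE count tables and the primary endpoints are not shown to change.

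The conclusion rests on a literal reading of Table 5-3 and on illustrative dates. The documents do not say how many partial end dates exist. SAP 4.2 puts enrolment at 15 patients, so the number of records may be small.

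**What to change.** In Table 5-3, replace both branches with one rule for all patients, whether they completed, discontinued or never took commercial everolimus in M2305:

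End date = earliest of 31 December of the recorded year (or last day of the recorded month), last contact or End of Study date, date of death and cut-off date, and never before the record's own start date.

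Use last dose plus 30 days only to assign AE onset to the exposure or post-exposure period. The rule no longer needs a last treatment date, so the gap left by SAP 2.1.2 does not affect it.

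With an assumed last contact of 30-Jun-2021, the record from 10-May-2019 would end on 31-Dec-2019. That is day 365 minus day 130 plus 1 = 236 days, instead of -755. The record from 15-Mar-2018 would run 292 days instead of -334.

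The SAP should also say whether the protocol's prevalence over time will be produced, since it is the protocol-specified AE analysis most exposed to end dates.

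The cost is SAP wording and a small programming change before database lock. No new data are needed.
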